Five dose levels are planned: [REDACTED] µg every 2 weeks (Q2W) (cohorts 1a), [REDACTED] µg every week (QW) (cohorts 2a), [REDACTED] µg Q2W (cohort 3), [REDACTED] µg QW (cohort 4), and [REDACTED] µg Q2W (cohort 5). Dose levels 1a ([REDACTED] µg Q2W) and 2a ([REDACTED] µg QW) will be enrolled concurrently. Three subjects each will be assigned to cohorts 1a ([REDACTED] µg Q2W) and 2a ([REDACTED] µg QW) alternately (total of 6 subjects). After the last subject completes the DLT evaluation period, a dose level review meeting (DLRM) will occur and if deemed necessary, 3 additional subjects each will be assigned to cohorts 1a and 2a alternately (total of 6 subjects) to gain additional information. After the last subject completes the DLT evaluation period, a DLRM will occur and if dose escalation is deemed appropriate, subjects will be enrolled in cohorts 3 ([REDACTED] µg Q2W) 4 ([REDACTED] µg QW), and 5 ([REDACTED] µg Q2W) as follows: first, 3 subjects will be enrolled in cohorts 3. An internal safety review will be conducted by the Amgen Medical Monitor and Global Safety Officer after the first 3 subjects complete the DLT evaluation period. If concerning safety issues are identified, a DLRM will occur to assess if it is safe to proceed with additional enrollment in cohort 3 and concurrent enrollment in cohort 4. If no concerning safety issues are identified in these first 3 subjects, enrollment of the remaining 3 subjects in cohort 3 will proceed without a DLRM. Concurrently, enrollment of 6 subjects in cohort 4 will begin with alternate assignment of subjects between cohorts 3 and 4 until enrollment of cohort 3

has completed. Enrollment of 6 subjects in cohort 5 will begin after the DLRM for cohort 4 is complete. DLRMs for cohorts 3, 4 and 5 will occur after the last subject in that cohort completes the DLT evaluation period.

[figure not shown]
All planned dose levels for a given cohort may be adjusted at any time based on emerging data. Additional dosing cohorts may be added, removed or substituted at any time based on emerging data and the results of continuous modeling. **As a result of a recommendation from an ad hoc DLRM, Amgen discontinued enrollment to cohort 5 at the planned [REDACTED] mcg Q2W dose. Subjects who were on-going at the time of this decision had their dose reduced to [REDACTED] µg Q2W for their remaining visits.**

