## **7.2 Final Analysis**

A final analysis will be performed after the end of the study, i.e., after the last subject in phase 1b part of the study completes the study (including the treatment period and safety follow-up period), or early terminates. All analyses described in Section 9 will be performed at this time. Analyses will be based on all available data.

Data will be subject to ongoing checks for integrity, completeness and accuracy in accordance with the Data Management Plan with the expectation that all outstanding data issues are resolved ahead of the final lock.

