#### 9.6.2.1 Dose Limiting Toxicities

The analysis of the probability of DLT will be based on the Dose Escalation part of the study defined in Section [3.1](#). A listing and summary of the subject incidence of DLT will be provided should they occur. After there is at least 1 DLT observed at any dose level, a Bayesian logistic regression model (BLRM) ([Bailey et al, 2009](#); [Neuenschwander et al, 2008](#)) will be used to inform dose escalation and the results of this analysis will be provided to the each DLRM. Three toxicity probability intervals (TPI) of DLT will be defined: target TPI (20% to 30%), excessive TPI (30% to 60%) and unacceptable TPI (60% to 100%). Adverse events meeting DLT criteria after week 4 and PD information may also be included in the model, as available. The model will recommend an MTD as the dose with highest probability in the target TPI, but with less than 25% probability in excessive TPI or unacceptable TPI. Lower dose levels, intermediate dose levels, or alternative dosing schedules may be considered based on all available information as long as they do not exceed the estimated MTD per the model.

Let  $\mathbf{d} = (d_1, \dots, d_k)$  denote the vector of all efavaleukin alfa doses to be studied in the study. The probability of a DLT at dose level  $d_i, i=1, \dots, k$  is assumed to follow a Bernoulli distribution with probability  $p_i$  where the logit of  $p_i$  increases linearly with the log of the standardized dose in the following 2-parameter logistic model:

$$\log \left[ \frac{p_i}{1 - p_i} \right] = \text{logit}(p_i) = \log[a] + \exp(\log[b]) \log\left(\frac{d_i}{\max(\mathbf{d})}\right)$$

where a and b are random variables and  $d_i$  is dose level represented by predicted

[REDACTED]  $d_k$  is an additional dose assuming Treg concentration = [REDACTED] that's higher than the currently planned doses. Thus  $\mathbf{d} = [REDACTED]$ . If additional dose cohorts were added during study conduct (e.g., decision following a DLRM), the value of  $\mathbf{d}$  will be updated.

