The probability of each TPI and of a DLT will be summarized by dose along with the estimated dose-toxicity curve. A final estimate of the MTD will be estimated from the Bayesian model by utilizing all DLT-evaluable subjects. Please refer to [Appendix C](#) for more details on the BLRM and its operation characteristics. Before each DLRM, the above BLRM will be fitted with the prior distribution as specified in [Appendix C](#). This model will only be used to aid DLRM dosing decision thus the recommendation of the model is non-binding in nature.

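### The final MTD rule in SAP 9.6.2.1 can name the top entry of the dose vector by default, even a strength nobody received, because it has no 'MTD not reached' outcome

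*SAP*

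**What the plan says.** SAP 9.6.2.1 fits a two-parameter Bayesian logistic model "After there is at least 1 DLT observed at any dose level". It then defines the selection: "The model will recommend an MTD as the dose with highest probability in the target TPI", with less than 25% posterior probability of an excessive or unacceptable rate. The named intervals are 20–30% (target), 30–60% (excessive) and 60–100% (unacceptable). Rates below 20% have no named interval.

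The same section builds the dose vector d and gives it a last entry, d_k, at a strength "that's higher than the currently planned doses". It allows d to be updated if cohorts are added. It then commits to a reported result: "A final estimate of the MTD will be estimated from the Bayesian model by utilizing all DLT-evaluable subjects". SAP 7.2 fixes the timing: "All analyses described in Section 9 will be performed at this time".

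Three other places bear on this:

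- SAP 9.6.2.1 says of the model as a dosing aid that "the recommendation of the model is non-binding in nature", and that interval probabilities and the dose-toxicity curve will be summarized by dose.
- SAP 3.1 records that, on the recommendation of an ad hoc dose level review meeting, "Amgen discontinued enrollment to cohort 5 at the planned" strength (value redacted).
- Protocol 4.1 includes estimating the MTD in the phase 1b primary objective. The primary objective in SAP 2.1 no longer mentions it.

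**The concern.** The rule picks a maximum over candidates and always returns one unless every candidate breaks the overdose limit. That exception is the only 'no MTD' result shown in the SAP (the row for all doses too toxic in Appendix C, Table 3). The opposite case, in which every studied strength looks too well tolerated to be the MTD, has no outcome. When DLTs are rare, the probability of a 20–30% rate is small everywhere and usually largest at the top of d. The top entry then wins by default, not because the data support it.

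At stake is a line in the final report. It could name as MTD a strength at which no subject was evaluated for DLT, and which lies above the level where enrolment stopped, while the same posterior says the DLT rate there is probably below target.

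**Working it through.** **Inputs.** From SAP Appendix C: logit(p_i) = log a + b·log(d_i / max d), with (log a, log b) bivariate normal, means −1.283 and 0.280, SDs 1.002 and 0.770, correlation −0.568. The intervals and the 25% limit are from 9.6.2.1. Cohorts of 3 to 6 are from 3.1. The strengths are redacted and neither the number treated in cohort 5 nor the DLT count is given, so these are assumed and varied. The base layout is five planned levels plus d_k, with nobody treated at d_k.

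**Reproducing the plan's own figures.** At the maximum dose log(d/max d) = 0, so P(p ≤ 0.50) = P(log a ≤ 0) = Φ(1.283/1.002) = 0.8998, against 0.90 stated. Strength ratios were then searched until Table 3 was roughly matched under the Appendix C escalation and stopping rules. With ratios 0.12, 0.35, 0.36, 0.45, 0.77 and 1 (1,000 simulated trials):

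| Table 3 row | Recomputed Low / Mid / High | Stated Low / Mid / High |
|---|---|---|
| Mean N | 14.8 / 19.3 / 23.4 | 14.8 / 19.7 / 23.0 |
| Acceptable MTD selected | 46 / 61 / 85% | 50.6 / 62.2 / 86.8% |
| All doses too toxic | 39 / 11 / 0.2% | 39.2 / 12.0 / 0% |
| Number of DLTs | 3.9 / 4.1 / 3.0 | 4.1 / 4.2 / 2.8 |

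The match is approximate and the ratios are not unique.

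**One DLT, by gap below d_k.** For each fit: compute the grid posterior, drop strengths with P(p ≥ 0.3) ≥ 0.25, and take the highest P(0.2–0.3). The DLT may fall in any of levels 1–5, with about 22–30 subjects. The two columns use different random spacings of the lower levels.

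| Cohort 5 strength / d_k | d_k named, set 1 | d_k named, set 2 |
|---|---|---|
| 0.6–0.95 | 99.9–100% | 97–100% |
| 0.5 | 97% | 97–100% |
| 0.4 | 89% | 97–100% |
| 0.3 | 51% | 77% |
| 0.25 | 11% | not run |
| 0.2 | 0% | 5% |

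With only 15 subjects, d_k was never named at ratios of 0.4 or below. In set 1, where d_k was named at ratios of 0.5 or more, the median posterior probability that its DLT rate is below 20% was 59–85%. Applying the 25% limit to each interval separately raises the share naming d_k slightly.

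**Grids matched to Table 3.** Five grids × five cohort layouts × five DLT positions = 125 one-DLT fits; d_k was named in all 125. At d_k, P(target) was 0.18–0.37, P(rate < 20%) 0.44–0.80 (median 0.63) and P(rate ≥ 30%) 0.02–0.20. By number of DLTs, d_k was named in 100% (one), 89% (two), 34% (three), 6% (four) and 0% (five).

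**If d ends at cohort 5's strength.** Over 400 assumed spacings × 30 layouts = 12,000 one-DLT fits, the rule names cohort 5's level in 11,958 (99.65%). The default moves down one level but remains.

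**Is restricting the candidates enough?** No. Limited to the five planned strengths, the same 125 fits all name the highest one. P(rate < 20%) there is 0.61–0.97 (median 0.86), which is the pattern of an MTD not reached.

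**The case against.** Several counter-arguments have weight.

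- *d_k may serve only to scale the model.* Appendix C points the other way: strengths were added to simulate a true MTD above the plan, and Table 3 scores selecting them as acceptable. No readable text removes them from the final estimate.
- *d_k may be cohort 5's own strength.* This cannot be excluded. Table 2's High column has its only two acceptable rates in the last two of six rows, which would fit four planned doses plus two, and Protocol 5.4 calls the cohort 5 dose additional. On that reading, a claim that nobody received the named strength fails. The default selection of the top entry does not.
- *The model is non-binding and meant only to aid dosing decisions.* That limits its force at dose review meetings. The final estimate is a separate promised output.
- *The interval probabilities are tabulated by dose.* True, and it helps: a careful reader would see the weak support beside the named MTD. It does not change which strength the report names.
- *The study is terminated, and the expansion cohort and phase 2 are cancelled.* This stands and lowers the severity, as does the SAP's narrower primary objective.

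A reader might infer that an untested MTD is near certain. The documents do not support that: the share depends on redacted spacings and falls with more DLTs. Nor is naming the top strength an error in Table 2's High scenario, where its true rate of 0.3 counts as acceptable. Nor does the cohort 5 stop show a contradiction: its reason is not given, and a DLT-defined MTD may differ from a decision made on other grounds.

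**Conclusion.** The point holds as a flaw in a stated reporting rule. The final MTD is chosen over a vector that reaches above the planned doses, with no requirement that the named strength was given and no 'not reached' result. With one DLT and roughly 22–30 subjects, the top entry is named in about 90–100% of fits when cohort 5's strength is at least 0.4 of d_k, about 50–80% at 0.3, and about 0–5% at 0.2. At ratios of 0.5 or more the posterior there usually favours a rate below 20%.

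These figures rest on assumed spacings, cohort sizes and DLT counts. If no DLT was observed, the model is not triggered and the rule is not applied. No printed figure is wrong, and nothing here bears on which dose is right. Severity is minor to moderate.

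**What to change.** Before database lock, add to SAP 9.6.2.1:

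1. The final MTD may be named only among strengths with DLT-evaluable subjects.
2. 'MTD not reached' is reported if the rule, run on the full vector, selects a strength that was not given, or if it selects the highest given strength and the posterior probability of a DLT rate below 20% there exceeds 50%.
3. Any result for d_k, if no subject was treated there, is shown only as a labelled extrapolation with its number of evaluable subjects (0).
4. A sentence on how the final estimate relates to the ad hoc meeting decision in SAP 3.1, and on its status now that SAP 2.1 omits the MTD from the objective. These passages need reconciling; no dose is proposed.

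In the 125 one-DLT fits on the Table 3-matched grids, item 2 gives 'not reached' every time: all 125 select d_k, and the lowest P(rate < 20%) at the highest planned strength is 0.61, above 0.50.

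The cost is a few sentences, with no patients, new data or re-simulation. The drawback is that the report may name no MTD.

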### **9.6.3            Laboratory Test Results**

#### **9.6.3.1        Chemistry and Hematology**

The analyses of safety laboratory endpoints will include summary statistics of baseline, post-baseline lab values at all the time points, change from baseline to post-baseline, post-baseline maximum/minimum and change from baseline to post-baseline maximum/minimum by dose level.

Shifts tables indicating the change between the baseline and the worst post dose CTCAE grades based on CTCAE version 4.03 or later will be provided for selected laboratory parameters of interest. Subject incidence of worst post-baseline eosinophils counts by the laboratory normal range will be provided.

**Chemistry and hematology laboratory tests performed by local laboratories will be included in the analyses where applicable in cases where central laboratory values were not obtainable (i.e. due to Covid restrictions).**

A listing of subjects identified as potential Hy's law cases (ALT or AST of >3xULN associated with total bilirubin > 2xULN and ALP <2xULN at a visit) will be provided with relevant laboratory tests included in the listing.

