6.1 Inclusion Criteria

For both phase 1b and [REDACTED] subjects are eligible to be included in the study only if all of the following criteria apply:

- 101 Subject has provided informed consent prior to initiation of any study-specific activities/procedures.
- 102 Subject is an adult \geq 18 years old at the time of signing the informed consent.

103 Subject is a recipient of an allogeneic HSCT.

104 Subject has moderate to severe steroid-refractory cGVHD as defined by all of the following criteria:

- Diagnosed with cGVHD per the 2014 cGVHD NIH Consensus Criteria (Jagasia, 2015; [Appendix 8](#)).
- Steroid refractory cGVHD, defined as having persistent signs and symptoms of cGVHD despite \geq 4 weeks of prednisone (or equivalent) dosed at \geq 0.25 mg/kg/day (or \geq 0.5 mg/kg every other day).
- Moderate to severe cGVHD (in accordance with 2014 cGVHD NIH Consensus Criteria [Jagasia, 2015; [Appendix 9](#)]) at screening with involvement of at least 1 of the following organs at the screening and baseline visits: skin, mouth, eyes, gastrointestinal (GI) tract, liver, lungs, and joint and fascia.

105 Subject has received no more than 3 previous treatments for cGVHD, excluding topical agents.

- Treatment with corticosteroids is considered a treatment for cGVHD and should be included in determining the number of previous treatments.
- Lines of therapy consisting of concurrent medications or interventions (eg, tacrolimus and corticosteroids; ECP and corticosteroids) count as 2 separate treatments.
- If cGVHD has worsened during a taper of immunosuppressive agents, restoring the agents to therapeutic level is permitted and does not count as an additional treatment.

106 Subject may be receiving corticosteroid therapy provided that the dose is \leq 1 mg/kg/day of systemic prednisone or equivalent and has been stable for at least 2 weeks prior to first dose of efavaleukin alfa.

107 Subject may be receiving other non-corticosteroid immunosuppressive therapies provided that the immunosuppressant dose is stable for at least 2 weeks prior to first dose of efavaleukin alfa. Adjustments to dose of calcineurin inhibitor or sirolimus are allowed only to maintain drug levels within therapeutic range.

108 Subject has a Karnofsky performance status score \geq 50%.

109 Subject has an estimated life expectancy of $>$ 3 months.

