10.4.2.3.3 Laboratory Test Results

The analyses of safety laboratory endpoints will include summary statistics at selected time points by dose level. Shifts in grades of selected safety laboratory values between baseline and the worst on-study value will be tabulated by dose level.

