Lung	Bronchiolitis obliterans diagnosed with lung biopsy Bronchiolans obliterans syndrome (BOS) ^d	Air trapping and bronchiectasis on chest CT	Cryptogenic organizing pneumonia (COP) ^e Restrictive lung disease ^e	
Muscles, fascia, joints	Fasciitis Joint stiffness or contractures secondary to sclerosis	Myositis or polymyositis ^f	Edema Muscle cramps Arthralgia or arthritis	-
Hematopoietic and immune	-	-	Thrombocytopenia Eosinophilia Lymphopenia Hypo- or hyper-gammaglobulinemia Autoantibodies (AIHA and ITP) Raynaud's phenomenon	-
Other	-	-	Pericardial or pleural effusions Ascites Peripheral neuropathy Nephrotic syndrome Myasthenia gravis Cardiac conduction abnormality or cardiomyopathy	-

Page 3 of 3

^a In all cases, infection, drug effect, malignancy, or other causes must be excluded.

^b Can be acknowledged as part of the chronic GVHD manifestations if diagnosis is confirmed.

^c Common refers to shared features by both acute and chronic GVHD.

^d BOS can be diagnostic for lung chronic GVHD only, if distinctive sign or symptom present in another organ.

^e Pulmonary entities under investigation or unclassified.

^f Diagnosis of chronic GVHD requires biopsy.

Source: Jagasia et al, 2015

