### **Overall summary of subject incidence of treatment-emergent adverse events and**

by preferred term and worst severity grade will be provided by anti-AMG592 and [REDACTED] status. Subject incidence of events of interest (standardized MedDRA queries and/or Amgen Medical Queries) will also be summarized according to their categories, preferred term, and worst severity grade. Events of interest could include but are not limited to Hypersensitivity, Tachyarrhythmias, Tachypnea, Hematopoietic Cytopenia, **Eosinophilic Disorder**, Leucocyte Changes, Infection and Infestation, Cytokine Release Syndrome, **Drug Related Hepatic Disorder**, and Injection Site Reaction. Number of episodes and duration of treatment-emergent injection site reactions will be further summarized.

Subject incidence of treatment-emergent adverse events identified by COVID-19 standardized MedDRA queries and serious adverse events occurring on or after the COVID-19 infection will also be summarized.

Subject incidence of disease related events and fatal disease-related events will be tabulated by system organ class and preferred term. They are defined for this study in [Appendix D](#).

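### The planned eosinophil incidence table has no baseline category, so it mixes eosinophilia present at entry with new onset and cannot by itself show treatment-emergent change

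*SAP*

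**What the plan says.** SAP 9.6.3.1 states: "Subject incidence of worst post-baseline eosinophils counts by the laboratory normal range will be provided". The sentence does not mention the subject's baseline state.

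Two other outputs in that section do use baseline.

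- Safety laboratory endpoints get summaries of baseline and post-baseline values, and "change from baseline to post-baseline, post-baseline maximum/minimum and change from baseline to post-baseline maximum/minimum by dose level". Eosinophils are in the hematology differential of Protocol Table 12-1, so these summaries cover them.
- "Shifts tables indicating the change between the baseline and the worst post dose CTCAE grades" are planned for selected parameters. Protocol 10.4.2.3.3 plans the same kind of output: "Shifts in grades of selected safety laboratory values between baseline and the worst on-study value will be tabulated by dose level". Neither document lists the selected parameters.

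The hematopoietic and immune row of Protocol Appendix 8 contains the entries "Thrombocytopenia Eosinophilia Lymphopenia". They stand in the column for other or unclassified features, with the footnote "Can be acknowledged as part of the chronic GVHD manifestations if diagnosis is confirmed". Inclusion criterion 104 requires confirmed disease: "Subject has moderate to severe steroid-refractory cGVHD as defined by all of the following criteria". The bone marrow criterion (114) covers neutrophils and platelets only, and no other criterion names eosinophils. SAP 9.6.2 lists "Eosinophilic Disorder" among possible events of interest. Protocol 7.2 describes the dose-ascending stage as single arm and open label.

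**The concern.** A table of incidence after the start of treatment is normally read as what happened on the drug. Here a subject above the normal range before the first dose, and still above it afterwards, enters the same cell as a subject who became high on treatment. The adverse event tables avoid this, because the SAP's definition of a treatment-emergent event requires onset on or after the first dose. This table has no such condition.

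With no control arm, each subject's own baseline is the main reference for attributing a change to the drug. Dosing cohorts have 3 to 6 DLT-evaluable subjects, so one or two carried-over cases change the percentage in a dose group noticeably. Chance differences between groups in eosinophilia at entry could then suggest a dose pattern, or mask one, in a finding that the sponsor has chosen to track.

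**Working it through.** **The plan's own figures.** The documents give no figure for eosinophils. The only detection figures are in the sample size sections, for an event with a true rate of 5%: 1 − 0.95^40 = 87.1% (stated as 87%) and 1 − 0.95^30 = 78.5% (stated as 79%). Both reproduce, and neither bears on this point. The same binomial formula is used below.

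**Inputs.** The group size of 6 is the upper end of the planned cohort range. The other three inputs are assumptions, because the documents give none of them:

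- b, the share of subjects above the normal range at baseline: 10% to 30%.
- q, the chance that such a subject is also above it at the worst post-baseline value: 1 or 0.7.
- d, the new-onset rate among subjects not high at baseline: 0, or 10% to 30%.

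Worst is taken to mean highest.

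**What the planned table reports.** Incidence above range = b·q + (1 − b)·d. The quantity of interest is d.

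**No drug effect (d = 0), group of 6.** Expected carried-over cases = 6·b·q. Chance of at least one = 1 − (1 − b·q)^6.

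| b | q | Expected cases | Chance of at least one |
|---|---|---|---|
| 10% | 1 | 6 × 0.10 = 0.6 | 1 − 0.90^6 = 47% |
| 30% | 1 | 6 × 0.30 = 1.8 | 1 − 0.70^6 = 88% |
| 10% | 0.7 | 6 × 0.07 = 0.4 | 1 − 0.93^6 = 35% |
| 30% | 0.7 | 6 × 0.21 = 1.3 | 1 − 0.79^6 = 76% |

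One such subject adds 1/6 = 17% to that group's reported incidence.

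**With a drug effect.** Take b = 20%, q = 1 and d = 20%. The table shows 0.20 + 0.80 × 0.20 = 36%, of which 0.20/0.36 = 56% was present at entry. Over b = 10% to 30%, q = 0.7 to 1 and d = 10% to 30%, the share present at entry runs from 0.07/0.34 = 21% to 0.30/0.37 = 81%.

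**Comparing dose groups.** Let X and Y be the numbers high at baseline in two groups of 6, each binomial with rate b. The chance that they differ by 2 or more is 13% at b = 10%, 27% at b = 20% and 34% at b = 30%.

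**With a baseline category.** Incidence among subjects not high at baseline estimates d directly, and is 0 when there is no new onset.

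**The case against.** The strongest reply is that the SAP does not ignore baseline for eosinophils. The same section plans change from baseline and change to the post-baseline maximum by dose level, and these address within-subject rise. That stands, and it limits the point to one missing presentation. It does not remove the point: under SAP 9.1 these are group means, standard deviations, extremes and counts of observations, and they do not give the number of subjects who crossed the upper limit. The dose level review meetings do receive subject-level listings and plots of laboratory data by cohort (SAP 7.1), but SAP 9.1 puts only critical listings in the study report.

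Eosinophils might also be among the parameters selected for shift tables. The documents neither include nor exclude them, and those shifts use CTCAE grades, not the normal range.

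Clinically relevant new eosinophilia could be reported as a treatment-emergent adverse event. That is true, but it depends on the investigator's judgment of clinical significance (Protocol 9.2.4).

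The baseline prevalence is assumed, and six subjects per group is not assured: cohorts may have as few as 3 evaluable subjects, and the SAP records that enrollment to cohort 5 at its planned dose was discontinued. Both statements are correct, so the percentages above are illustrations and not estimates for this trial.

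Finally, nothing formal depends on the table. It supports no hypothesis test, and the hematological DLT criterion concerns falls in neutrophils or platelets. That stands, and it sets the severity.

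**Conclusion.** The point holds as a minor one. As written, the table counts eosinophilia present at entry together with new onset, and the two cannot be separated from it. Under an assumed baseline prevalence of 10% to 30%, a group of 6 would be expected to show 0.6 to 1.8 cases with no drug effect if all those subjects stay high. The effect disappears if nobody enters above the range.

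A reader might go further and infer that the table measures only existing disease and says nothing about the drug. The documents do not support that: the table shows a mixture, and its split depends on a prevalence they do not give. Nor do they say that chronic GVHD causes eosinophilia in these subjects. Appendix 8 lists it as a feature that may be acknowledged once the diagnosis is confirmed, without a frequency. The disease-related event tables (Protocol Appendix 11, SAP Appendix D) have no hematologic entry, although the protocol says that its list is not comprehensive.

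The consequence is confined to how one descriptive safety output is read.

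**What to change.** In SAP 9.6.3.1, replace the eosinophil sentence with a cross-tabulation of worst post-baseline category (below, within or above the laboratory normal range) by baseline category and dose level. State that worst means the highest count for the above-range result. Beneath it, report the number and percentage above the upper limit among subjects who were not above it at baseline, with that number of subjects as the denominator. Keep the continuous change-from-baseline summaries, which show further rises in subjects already high.

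The cost is one SAP sentence and one table shell. No new data are needed: SAP 5.1 already defines baseline, and Protocol Table 2-1 schedules hematology at screening and at the baseline visit.
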